10.3 POSTOPERATIVE STUDY DAY 1-21 OR TO HOSPITAL DISCHARGE

Mass balance sampling and calculation will continue up to hospital discharge or at most for 21 days after the surgical procedure. POD 1 ELISAs will be taken in all study patients. POD 4 also in adults not in the ICU.

10.4 POSTOPERATIVE STUDY DAY 4 -21 IN ICU

If an adult patient is in the ICU after POD4 measurement of albumin synthesis rate will be performed by the flooding method. The exact time point will be to the discretion of an investigator. In the semi-recumbent position measurements of albumin synthesis rate (11.3) is performed over 90 minutes. Also a blood sample for ELISAs will be taken. The procedure can be repeated once or twice for measurement of albumin synthesis rate but only within the permitted total sampling blood volume (100 ml).

Children in ICU after POD 4 can be subject to ELISAs (2+2 ml).

11 METHODS AND ANALYSIS

11.1 ALBUMIN MASS BALANCE

[figure not shown]
During preparations before surgery and during the surgical procedure blood samples for albumin concentration determination will be taken at the same time intervals as routine blood gases. Thereafter sampling interval will be 1-2 times per day. In parallel all fluid losses will be collected, measured and documented, sampled and saved for analysis. Also, infusions containing albumin or hemoglobin will be monitored.

11.2 ALBUMIN CONCENTRATION

Albumin concentrations in plasma will be measured employing nephelometry at Studieceter at Karolinska University Hospital. Albumin in other fluids (X-alb) will be analyzed at Karolinska Stable Isotope Core Facility at KFC Novum.

11.3 ALBUMIN SYNTHESIS RATE

To measure albumin synthesis rate an infusion of D5-phenylalanine 20 mg/mL 10 MPE, 0.45 g/kg will be given over 10 minutes. A 90-minute blood sampling protocol for determination of the ratio D5-phenylalanine/phenylalanine and the incorporation of D5-phenylalanine into albumin will be applied as illustrated in Figure 1. Analysis is performed by gaschromatography-massspectrometry (GC-MS) at Karolinska Stable Isotope Core Facility at KFC Novum. The fractional synthesis rate (FSR) is expressed as %/24 hours of albumin in plasma, while the absolute synthesis rate (ASR) expressed as mg/kg/24 hours, can be calculated if also plasma volume (from anthropometry) and plasma albumin are known.

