5.3 ALBUMIN MASS BALANCE CALCULATIONS

By rigorous measurement of losses and gains of albumin during and after surgery, i.e. assessing bleeding, losses in drains, urine etc and measuring hemoglobin and albumin in plasma samples and in all blood products given, it is possible to calculate the loss of albumin from plasma that is not accounted for by other means. This is the cumulative perioperative albumin shift (CPAS) that represents albumin lost from the blood by capillary leakage or catabolism.

In major gynecological cancer surgery protein loss was reported as 49 g [Rehm 1998], and after major abdominal surgery cumulative perioperative albumin shift was 19 g (range 2-61) [Norberg 2015]. In liver transplantation the perioperative albumin loss was 37 ± 17 g (EPN D-nr 2015-1048-31/2, preliminary results) at end of surgery.

Blood sampling outside clinical routine for albumin mass balance calculations will not exceed 40 ml during a 21 day period. For children there is no study specific blood sampling at all for the mass balance analysis.

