5.4 ALBUMIN DE NOVO SYNTHESIS

Albumin is synthesized in the liver at a rate of 150 mg/kg/day, or 13 g/24 h [Barle 2002]. This corresponds to a fractional synthesis rate of 6-8 %/24 h in a healthy subject with a plasma volume of 3 liters and 120 g of albumin in the intravascular space [Kaysen 1998]. In addition there is another 180 g of albumin in the interstitial space. These two compartments are in equilibrium by capillary leakage of 5 % per hour that is returned to the vascular space through the lymph flow. In states of an increased capillary leakage or circulatory instability, these figures may be dramatically altered [Margaron 2002].

Albumin synthesis rate is determined by incorporation of isotopically labeled amino acids into albumin [Ballmer 1990]. Today the most common technique is to use deuterated phenylalanine given as a flooding dose. De novo synthesis of albumin is stimulated by food intake, while it is decreased in states of liver insufficiency [Caso 2007, Ballmer 1996].

The blood sampling volume for one measurement of albumin synthesis will be 20 ml.

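### Read literally, the tracer instruction in section 11.3 is 22.5 mL/kg in 10 minutes (1,575 mL at an assumed 70 kg); verify the amount per kg and the concentration, and correct the wrong one

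*Combined protocol and SAP*

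**What the plan says.** The whole visible dosing instruction is one clause in section 11.3: "an infusion of D5-phenylalanine 20 mg/mL 10 MPE, 0.45 g/kg will be given over 10 minutes". Sections 5.4, 9, 10.4 and 15.2 mention the tracer or the method without a dose. Section 11.3 refers to Figure 1 for the sampling scheme, and section 25.1 lists a flow chart; neither is visible in the text reviewed.

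The recipients are defined in section 10.4: "If an adult patient is in the ICU after POD4 measurement of albumin synthesis rate will be performed by the flooding method". The same section allows one or two repeats. The limit it sets, 100 ml, is on blood drawn and not on fluid given. Section 17.3 expects about 20 adults with a prolonged ICU stay.

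Section 5.4 explains the method: "the most common technique is to use deuterated phenylalanine given as a flooding dose". Section 14 says that the tracers serve measurement and are not treatment. Section 15.2 provides for vital-sign monitoring before the tracer and for 90 minutes after it.

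**The concern.** Amount per kg, concentration and infusion time together fix the volume and the rate. Here they imply a litre-scale infusion in 10 minutes, in patients whose ICU stay is already prolonged after a liver transplant and who gain nothing therapeutically from it. The background in section 5.1 itself links gross fluid overload with poor outcome in surgery and critical illness.

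A flooding dose is deliberately large, so the gram amount alone proves nothing. The volume and the rate are what look implausible. Because this is the operative instruction and no visible text gives a second figure, a reader preparing the infusion has nothing in the protocol against which to catch a slip. The monitoring in section 15.2 can detect a reaction, but it does not check the dose.

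**Working it through.** **Inputs from the documents**
- Amount: 0.45 g/kg = 450 mg/kg (section 11.3)
- Concentration: 20 mg/mL (section 11.3)
- Infusion time: 10 minutes (section 11.3)
- Yardstick for scale: "a healthy subject with a plasma volume of 3 liters and 120 g of albumin in the intravascular space" (section 5.4)
- Expected number of prolonged-ICU adults: about 20 (section 17.3)

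**Assumption.** Body weight is not given. I use 50, 70 and 90 kg.

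The plan states no volume, so there is no figure of its own to reproduce.

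**Step 1. Volume per kg.** 450 mg/kg ÷ 20 mg/mL = 22.5 mL/kg.

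**Step 2. One infusion.** Volume = 22.5 × weight; rate = volume ÷ 10; grams = 0.45 × weight.

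| Weight (assumed) | Volume | Rate | Phenylalanine | Volume ÷ 3,000 mL |
|---|---|---|---|---|
| 50 kg | 1,125 mL | 112.5 mL/min | 22.5 g | 37.5% |
| 70 kg | 1,575 mL | 157.5 mL/min | 31.5 g | 52.5% |
| 90 kg | 2,025 mL | 202.5 mL/min | 40.5 g | 67.5% |

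The last column shows scale only. It compares the volume with a healthy person's plasma volume and does not say how much would stay in the circulation. No weight in this range brings the volume below a litre.

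**Step 3. Repeats, at 70 kg.** Endpoint 8.2 C has two windows (POD 4-6 and POD 7-14). Two infusions are 2 × 1,575 = 3,150 mL and 2 × 31.5 = 63 g. Section 10.4 would permit a third: 3 × 1,575 = 4,725 mL and 94.5 g. That is a ceiling and not the expected course. Over 20 adults the count is 20 infusions with one each, 40 with two, and at most 60.

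**Step 4. Can another reading rescue the line?** Suppose 20 mg/mL counts only labelled phenylalanine, while 0.45 g/kg counts all phenylalanine at roughly 10% label. Then 450 × 0.10 ÷ 20 = 2.25 mL/kg, or 157.5 mL at 70 kg. The text does not say this. It would mean a solution of about 200 mg/mL total phenylalanine, and the grams would still be 31.5 at 70 kg.

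**Step 5. Why the volume alone cannot settle it.** As an illustration only, take two single-figure changes at 70 kg:
- 45 mg/kg at 20 mg/mL: 45 × 70 ÷ 20 = 157.5 mL, carrying 3.15 g
- 450 mg/kg at 200 mg/mL: 450 × 70 ÷ 200 = 157.5 mL, carrying 31.5 g

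The volume is the same and the mass differs ten-fold. The documents support neither figure as the intended one.

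**The case against.** The strongest reply is that nothing in the documents makes the written volume unsafe. They give no limit on volume, rate or phenylalanine. The only yardstick is a healthy plasma volume, and the remark on fluid overload is background without a threshold. This stands in part: calling the line implausible and unsafe is a clinical judgement drawn from its scale and from the recipients.

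A second reply is that this is only a typing slip. Section 5.2 reports a pilot in which synthesis rate was measured, so the team has used the method before. If staff use their established preparation, the patient never receives the written volume. That lowers the risk of actual harm, but the pilot dose is not given and the written instruction remains wrong or unclear. Figure 1 or the flow chart might carry a volume. If it differed from 22.5 mL/kg, section 11.3 would still need correcting.

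Third, section 17.1 already places ICU and ward medication lists, and a record of vital parameters at tracer administration, in the CRF. This is partial cover, since tracer mL and grams are not expressly listed. It may make a retrospective check easier.

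A reader might also infer more than the text supports:
- **An internal contradiction.** There is none. The three figures are arithmetically compatible; the question is whether the resulting dose is credible.
- **Bias in the primary endpoint or in sub study B through diluted plasma albumin.** This would need the written volume actually given, an unknown fraction still in plasma when the sample is drawn, and no correction through the hemoglobin measured under section 5.3. In sub study B, the EOS and POD3 comparisons precede any infusion, so only POD7 (4-10) could be touched at all.
- **A blood-volume breach.** The 100 ml ceiling concerns samples drawn and has no bearing on the dose.

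**Conclusion.** The point stands, and the line must be corrected on the strength of the literal instruction alone. As written, section 11.3 orders 22.5 mL/kg in 10 minutes, with no visible cap on infused volume. The arithmetic assumes that both figures refer to the same phenylalanine mass; the total volumes also rest on assumed body weights, and the conclusion is the same across 50 to 90 kg. The labelled-tracer-only reading of 2.25 mL/kg is strained and unstated, but an instruction open to a ten-fold difference in volume needs clarifying in any case.

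Two things are not established: which figure is wrong, and whether any patient received the written volume. A ten-fold slip in the amount per kg is possible, but the documents do not show it. Confidence that the line needs correcting is therefore higher than confidence that harm occurred. The statistical reach is limited to the synthesis-rate measurements under 8.2 C in about 20 adults.

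**What to change.** Before further use, check both the amount per kg and the concentration against the tracer preparation record, and correct the wrong figure in section 11.3. State there whether the concentration refers to total or labelled phenylalanine, the resulting mL/kg, and a maximum volume per infusion. I propose no replacement dose, because the documents do not show the intended one.

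If infusions have already been given, confirm the administered mL and grams from the records of the prolonged-ICU adults concerned.

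The cost is a short correction to section 11.3, with ethics notification if required, and at most a record check in about 20 patients. Enrolment, sampling volumes and the sample size do not change.

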11.4 SAMPLE HANDLING

Samples for GC-MS and ELISA analysis are anonymized and kept in Stockholms Medicinska Biobank reg nr 914 at Perioperative Medicine and Intensive Care at Karolinska University Hospital Huddinge, at -80°C pending finalization of study to be analyzed in one sequence to optimize precision in accord with our local routines. Samples for albumin analysis will likewise be marked in a non-identifiable way and kept in the biobank at -20°C pending finalization of study to be analyzed in one sequence to optimize precision in accord with our local routines.

Dr [name] will be the responsible person for sample handling, anonymization and destruction after publication. The responsible organization for personal data is Stockholm City Council, [name].

12 SUBJECTS

12.1 INCLUSION CRITERIA

Patients undergoing liver transplantation: adult males and females, and children 0-17 years.

Written informed consent. In children below 12 years consent is only obtained from the parents.

- A. Adults (mass balance, albumin synthesis and ELISAs)
- B. Children (only assessment of losses and gains, no blood sampling except for ELISAs)

12.2 EXCLUSION CRITERIA

Circumstance that makes the investigator judge patient participation unsuitable, mainly inability to understand study information (language difficulties or encephalopathy)

13 CRITERIA FOR DISCONTINUATION

13.1 PATIENT RELATED CRITERIA

- The patient may, at any time during the study, chose to end his/hers further participation in the study, without giving any cause.

If possible, the reason for discontinuation shall be stated in the CRF with date and time.

13.2 INVESTIGATORS CRITERIA AND EVALUABILITY

The primary investigator can determine that the patient cannot stay in the study. This can be founded on lack of evaluability or the reasons stated below:

- Errors in technical equipment
- Staff shortage that makes safe and standardized methods impossible.

The reason for discontinuation shall be stated in the CRF with date and time.

13.3 SUBJECT LOG

The investigator will keep a record of all eligible patients on a log list. The log list is stored in the investigator brochure available Perioperative Medicine and Intensive Care at Karolinska University Hospital Huddinge, in a locked room. It will show all screened subjects, included and not included.

14 TREATMENT

There is no study specific treatment. Study tracers are only used to monitor body physiology, not to treat the patient.

15 ASSESSMENT OF SAFETY AND EFFICACY

The patients are monitored according to local routines at Karolinska University Hospital Huddinge. No external monitoring related to this study is planned.

15.1 ASSESSMENT OF ANALYSIS RESULTS

Laboratory will be analyzed at the ISO certified Karolinska University Laboratory, Huddinge. Blood gases are analyzed at the Department of Anesthesiology. P-albumin will be analyzed by immunochemical method through the Studiecenter at the Karolinska University Laboratory, Solna. X-albumin and ELISAs will be performed at Karolinska Stable Isotope Core Facility at KFC Novum.

15.2 ASSESSMENT OF PATIENT SAFETY

Patients will be monitored in the operating room, at the intensive care unit and at the transplant surgical ward, respectively, for the mass balance sampling. Stable isotopes will be administered in the ICU or in the transplant surgical ward by a staff that is familiar with emergency incidents. Monitoring of the patient's heart rate, ECG, respiratory rate, oxygen saturation (oximetry), and blood pressure are taken before and during the first 90 min after administration.

15.3 ASSESSMENT OF ANALYSIS RESULTS

Laboratory samples, taken during and after surgery, are analyzed at the ISO certified Karolinska University Laboratory, Huddinge. Blood gases are analyzed by analyzers at the Department of Anesthesiology and Intensive Care Unit, respectively. P-albumin will be analyzed by immunochemical method through the Studiecenter at the Karolinska University Laboratory, Solna. ELISAs and X-albumin (blood products, drains etc) will be analyzed at Karolinska Stable Isotope Core Facility at KFC Novum. Other samples are analyzed as described in paragraph 11.

16 MANAGEMENT AND REPORTING OF ADVERSE EVENTS

All patients undergoing a liver transplantation will in the perioperative course experience incidents that would under other circumstances be described as AE/SAE. Major surgery in itself is associated with hospitalization. Therefore expected effects of anesthesia and surgery will not be reported, even if they may be considered undesirable. Such effects do not relate to the planned measurement procedures and they are not controlled by the investigator. Given the observational character of the study However, events that may influence the results of the study or whether subjects are evaluable or not will be noted in the CRF.

17 STATISTICS AND DATA MANAGEMENT

17.1 DATA MANAGEMENT

All laboratory values will be printed from the patient record (Take Care, TC) de-identified and attached to the CRF. All values of vital parameters during in connection with tracer administration will be documented directly on a coded anesthesia paper record by the research nurse or the investigator. This journal is a part of the CRF. Other documents that are stored in the CRF for coding and de-identification are: medical record from the Department of Transplant Surgery, medication list from TC, medication list from CliniSoft (the medical record system at the Intensive Care Unit).

Data from the mass spectrometer measurements of phenylalanine will be exported as a data sheets via a USB stick.

All the data regarding end-points will be added in an Access database that is locked when data collection is complete.

De-identified and coded patient demographics will be prepared and included in the Access database.

17.2 STATISTICAL ANALYSIS

In a previous study on selected patients undergoing liver transplantation at our department, we found a net leakage of albumin of 37 ± 17 g at end of surgery and of 48 ± 33 g at the third postoperative day. In our hospital, post-operative albumin infusions to keep plasma albumin at 25 g/l are very common, suggestive of ongoing losses in this patient group.

The effect and time course of ischemic liver injury on albumin synthesis has not been investigated, but in the previous pilot study albumin synthesis was higher than normal values on post-operative day 3. All data will be presented as mean with standard deviation (SD) or as median and range of data if not normally distributed.

Furthermore, the mutual correlations between the mass balance albumin parameters and albumin synthesis and P-albumin will be calculated and presented with correlation coefficients. Patients will be dichotomized to “leaky” and “not so leaky”, and possible predictors analyzed by univariate and multivariate logistic regression.

With 103 subjects there is a power of 80% to detect an anticipated effect size of 0.11 with 3 predictors and a 2-sided significance level of 5%. This equals the situation where the 3rd predictor gives an increase in the squared correlation coefficient r^2 from 0.30 to 0.37 or from 0.50 to 0.54. Although this is rather hypothetical it seems likely that such inferences might occur, and we will find them if 2 years production of liver transplants are investigated. If only 2 predictors are used an effect size of 0.095 can be found with 80% power.

Correlations will be reported as Pearson's correlation coefficient r or Spearman's rank correlation r_s depending on the data's nature.

Demographic preoperative data such as age, height, weight, BMI, gender, routine lab, history of weight loss, diagnoses, and current medications will be presented as numbers, averages and standard deviation, or as median range as applicable.

17.3 DETERMINATION OF THE NUMBER OF SUBJECTS

On page 4 we state that the number of subjects is 240 in the main study. This refers to an overestimation of the total number of liver transplantations during a approximately 2 year period at our hospital and the primary outcome of albumin mass balance.

The primary endpoint of the study (cumulative perioperative albumin shift at POD7) has never been investigated before. On POD3 48 ± 33 g, $p=0.0017$ versus baseline was found in our previous study on selected patients undergoing liver transplantation [Amouzandeh 2017]. This corresponds to a effect size of 1.4. Although data in consecutive patients are likely to be even more scattered a power of 90% is reached with $n=100$ for an effect size of 0.33 with a one sample 2-sided t-test and a significance level of 5%.

We plan to do linear regression with the thus detected “leakiness” as dependent variable and look at possible predictors. We will also dichotomize the patients in “leaky” and “not so leaky” (cut off to be estimated by ROC-curve analysis) and explore possible predictors by logistic regression and multiple logistic regression. The size of the data base becomes important to the quality of the multiple regression procedure, but data quantity will be governed by our patient flow and research resources. Data collection over much more than 2 years is likely to be confounded by changes in routines over time.

The large number of correlations mentioned above must be seen against the background that this is an exploratory pilot study of albumin mass balance and albumin kinetic parameters in liver transplantation. Because this is an unselected patient group for this kind of measurements, there is an intention that the study also should be hypothesis generating.

Sub study A (children, n=20) is included in the above mentioned number.

Sub study B (prolonged ICU stay, n=20) is a cohort included in the main study above.

The expected numbers in substudies A and B are the main reason to extend the whole study to approximately 2 years, and are based on historical records. Although data are likely to be scattered, with n=10-20 there is a reasonable chance to perform statistical inference analysis. The groups will also be compared with the complete data set.

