7.2 SECONDARY QUESTIONS

1. Does perioperative loss on POD7 (4-10) correlate to losses at EOS and POD3?
2. Is cumulative perioperative loss of albumin from plasma still positive at hospital discharge (or POD 21) following liver transplantation?
3. Dichotomize patients in two equally sized groups depending on the amount of cumulative loss of albumin from plasma on EOS, POD3 and POD7 respectively, i.e. to a "leaky" and a "less leaky" group. Which factors predict "leakiness" (demographics, bleeding, fluid balance, ascites, ELISAs etc)?

4. Is cumulative perioperative loss of albumin from plasma positive at EOS, POD3 and POD7 (4-10), respectively, after liver transplantation in children? This is the primary question in the children substudy .
5. Does perioperative loss on POD7 (4-10) correlate to losses at EOS and POD3 in children after liver transplantation?
6. Which factors characterize children with large postoperative drain losses after liver transplantation?
7. Does cumulative perioperative loss of albumin from plasma at EOS, POD3 and POD7 (4-10), respectively, differ between adults in need or not in need of prolonged ICU stay, respectively, after liver transplantation? This is the primary question in the prolonged ICU substudy.
8. Which factors predict “need of prolonged ICU stay” after liver transplantation (demographics, bleeding, fluid balance, ascites etc)?
9. How does synthesis rate of albumin develop during prolonged ICU stay?

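### The 'leaky' outcome of the logistic predictor models has two conflicting cut rules: equal halves in 7.2, and in 17.3 a ROC cut-off that cannot be run as written

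*Combined protocol and SAP*

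**What the plan says.** Three places in the combined protocol and SAP deal with the dichotomy.

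- Section 7.2, question 3: "Dichotomize patients in two equally sized groups depending on the amount of cumulative loss of albumin from plasma". This is to be done at end of surgery (EOS), POD3 and POD7 separately, and the question is then which factors predict leakiness.
- Section 17.2: patients are dichotomized and "possible predictors analyzed by univariate and multivariate logistic regression". No cut rule is given.
- Section 17.3: "We plan to do linear regression with the thus detected" leakiness as dependent variable. Patients will also be dichotomized, with the "cut off to be estimated by ROC-curve analysis", and predictors explored by simple and multiple logistic regression.

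Identifying predictors of albumin loss is part of the study aim in the Summary and a secondary aim in 6.1. Section 17.3 also calls the study an exploratory pilot that is meant to generate hypotheses.

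**The concern.** The equal-halves rule and the ROC rule define the same dependent variable for the same purpose, and they agree only if the ROC cut happens to fall on the sample median. No section says that one of them prevails or is a sensitivity analysis.

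The ROC rule is also incomplete. A ROC curve shows how well a continuous measure separates two states that are known from elsewhere. Without a named state there is no curve, and without a criterion there is no cut-off on it. Whoever runs the analysis would have to supply both, with the data in hand. If the cut were placed where a candidate predictor separates the groups best, that predictor would then be tested against an outcome it had helped to define. What is at stake is the outcome definition of the 'leaky' logistic models, and so the odds ratios from those models.

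**Working it through.** The plan states no figure for this point, so the check is a comparison of the text, followed by a small illustration.

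**1. The two rules side by side**

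| | 7.2, question 3 | 17.3 |
|---|---|---|
| Cut | two equal groups, in effect the median | ROC-derived |
| Reference outcome | none needed | needed, none named |
| Criterion | fixed by the rule | not given |
| Time point | EOS, POD3 and POD7 | not given |
| Share 'leaky' | 50% by construction | unknown |

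Section 17.2 leaves every row open.

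**2. Could the reference outcome be inferred?** Section 7.2 contains other two-state descriptions of patients: a loss still positive at discharge (question 2), large drain losses in children (question 6), and whether losses "differ between adults in need or not in need of prolonged ICU stay" (question 7, with its predictors in question 8). None is linked to the ROC analysis. The paragraph before the ROC sentence in 17.3 concerns POD7, so POD7 may be the intended time point, but the text does not say so.

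**3. How many patients could change group (illustration)**

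Inputs: N = 103, the number in the regression statement of 17.2 ("With 103 subjects there is a power of 80% to detect an anticipated effect size of 0.11 with 3 predictors"), used here only as a convenient size; and an assumed 'leaky' share P under a ROC cut, for which the documents give no value.

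Both rules cut the same ranking of patients, so the number classed differently is |0.50 − P| × N.

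- P = 45%: 0.05 × 103 = 5.15, about 5 patients
- P = 40%: 0.10 × 103 = 10.3, about 10 patients
- P = 30%: 0.20 × 103 = 20.6, about 21 patients
- P = 20%: 0.30 × 103 = 30.9, about 31 patients

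The formula is symmetric: a share of 70% would also move about 21 patients, in the other direction.

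**The case against.** The strongest reply is that little depends on this. It is one secondary analysis in a study declared exploratory. The primary endpoint uses no cut. Section 17.3 plans linear regression on continuous leakiness before it mentions the dichotomy, and that analysis serves the predictor aim without any cut. All of this stands, and it limits the weight of the point. It does not remove the conflict: the logistic models are planned in both 17.2 and 17.3, question 3 of 7.2 asks for the dichotomy, and exploratory status does not make two different outcome definitions one.

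It can also be said that a median in grams is itself known only once the data are in. That is true, but the median rule is fixed in advance and leaves nothing to choose. The ROC rule leaves the reference, the criterion and the time point open.

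A reader might infer more than the documents support, in two ways.

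- *That every odds ratio in the study is affected.* Question 8 of 7.2 asks what predicts prolonged ICU stay, and any odds ratios there do not use the 'leaky' cut.
- *That the conflict would overturn a large share of the predictor findings.* Simulation can seem to show this. With a normal outcome, three independent predictors, the r² scenarios of 17.2 and 103 patients, the significance verdict on the third predictor differs between the median split and a 30% or 20% cut in about 28% to 41% of runs. Those shares are assumed. At shares of 40% to 45% the range is about 14% to 25%. The median-split logistic model also disagrees with the linear regression already planned in about 23% to 34% of runs. Much of the disagreement therefore comes from limited power and from dichotomizing at all, so these rates do not measure the effect of the conflict.

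**Conclusion.** The inconsistency is real and lies in the current text: 7.2 and 17.3 give different rules for the same outcome, 17.2 gives none, and the rule in 17.3 cannot be carried out as written. As it stands, the outcome of the 'leaky' logistic models could be chosen after the data are seen. This conclusion rests on the wording alone.

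The size cannot be fixed from the documents, because they do not say where a ROC cut would fall. The 21 or 31 of 103 patients hold only for assumed shares of 30% or 20%; a share close to 50% would move few patients. The primary endpoint, the linear regression on continuous leakiness and the prolonged-ICU question are unaffected. This is a minor inconsistency in a secondary analysis that should be settled before the data are analysed.

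**What to change.** In 17.3, replace the ROC cut-off with the equal-halves (median) split at EOS, POD3 and POD7, as in 7.2, question 3. In 17.2, where the logistic models are described without a cut, refer to that rule.

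If a ROC analysis is still wanted, name its reference outcome, criterion for the cut and time point in advance, and report it separately from the predictor models.

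The cost is one sentence in 17.3 and a cross-reference in 17.2, with no new data and no change to the sample size. The drawback is that a median cut has no clinical meaning in itself. It is, however, the plan's own rule in 7.2, and the continuous regression remains alongside it.
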